8.1.3 Conditions Existent Before the Start of the Period of Collection (ICF Signature)

Clinical conditions that existed before the start of the period of collection (concomitant disease), and whose severity remained unchanged after that point, should not be considered AEs and should not be captured as such. This includes medical therapies or surgical interventions that had been planned before the start of the period of collection regardless of involving admissions to hospital, if the medical condition to be addressed did not get worse after that point. Otherwise, any medical condition that existed before the start of the period of collection and whose severity or frequency increased after that point is to be captured as an AE or SAE, depending on the seriousness criteria met.

8.2 Assessment of Adverse Events

8.2.1 Collection of Information

Any non-serious AE occurrence during the study must be documented in the subject's medical records in accordance with the Investigator's clinical practice and on the AE page of the CRF. SAEs that occur during the study must be documented in the subject's medical record, on the AE page of the CRF, and on the SAE form.

AEs should be collected mainly via face-to-face interview with the subject through spontaneous reporting or by the use of consistent, open, non-directive questions from the investigational site collaborators (e.g., "Have you had any health problems since you were last asked?" or "How have you been feeling since you were last asked?").

Information recorded will include: verbatim description of the AE/SAE, start and stop dates, seriousness, severity (intensity), action taken (e.g., whether or not the AE/SAE led to the subject's discontinuation from the study), and outcome (e.g., resolved).

Information to be recorded about an SAE should also include, whenever possible, onset and resolution dates and times, circumstances leading up to the event, clinical elements such as clinical course, specific vital signs and test results that may explain the pathophysiology of the event, as well as alternative explanations to its occurrence.

Whenever a medically meaningful diagnosis is available to comprise a set of reported signs and/or symptoms, it should be preferentially provided as the AE or SAE term, rather than the individual signs and/or symptoms. Otherwise, each one of those signs and/or symptoms should be reported separately as event terms.

8.2.2 Period of Collection

Any AEs which occur during the Screening period will be captured by the study site staff and assessed by the Investigator or designee(s) in order to establish relationship to study procedures.

AEs (including SAEs) will be collected from the time of ICF signature until the end of the study (EOS). AEs (including SAEs) will be collected from the time of ICF signature until the EOS.

During a 7-day passive safety FU, there will be recording of spontaneously reported new AEs/SAEs and the active follow-up of ongoing AEs/SAEs by the study site. In general, all AEs will be followed-up until resolved, stabilized (i.e., no worsening of the event), or a plausible explanation for the event has been found and until the end of the study.

Any AEs or SAEs that are ongoing at the end of the passive safety FU will be managed as described in [Section 8.2.6](#).

SAEs spontaneously reported to the PI after the end of the passive safety FU and considered related to the IP must also be reported to the Sponsor.

Data and information contained in this document are considered to constitute trade secrets and confidential commercial information, and the legal protections provided to such trade secrets and confidential information are hereby claimed under the applicable provisions of US law. No part of this document may be publicly disclosed without the written consent of PMI.

8.2.3 Intensity of Adverse Event

The Investigator must assess the intensity of each reported AE according to the following grading scale:

- Mild:** Easily tolerated, not interfering with normal everyday activities.
- Moderate:** Interferes with normal daily activity, but the subject is still able to function.
- Severe:** Incapacitating and requires medical intervention.

8.2.4 Relationship to Investigational Product and Relationship to Study Procedures

The Investigator must assess the causal relationship between the exposure to the IP and each of the reported AEs, using the classification system and the criteria described below. The same assessment must be made separately to assess the causal relationship between the study procedures and each of the reported AEs:

- Not related:** The temporal relationship of the adverse event to IP administration or study procedure(s) makes a causal relationship unlikely, or, concomitant medication, therapeutic interventions, or underlying conditions provide a sufficient explanation for the observed event.
- Related:** The temporal relationship of the adverse event to IP administration or study procedure(s) makes a causal relationship possible, and concomitant medication, therapeutic interventions, or underlying conditions do not provide a sufficient explanation for the observed event.

8.2.5 Expectedness

Any AE assessed as related to the IPs will be assessed for its expectedness. An AE will be regarded as “unexpected” if its nature or severity is not consistent with the information already recorded about the IP P4M3 in Section 6.5 of the current IB.

Table 3 presents expected AEs for the subjects’ own e-cigarettes.

**Table 3. Expected AEs: Foreseeable Risks with Subjects' Own e-Cigarette Use**

Risks Associated with:	Potential Adverse Events
Over-exposure to nicotine / nicotine acute intoxication / poisoning	Mild intoxication : Nausea, hyper-salivation, abdominal pain, vomiting, diarrhea, cold sweat, diaphoresis, headache, dizziness, hearing and visual disturbances, mental confusion, agitation, tremor, weakness, weak analgesia, increase of respiratory reflex and coughing, increase bronchial secretions, shortness of breath (as a consequence of stimulation of lung mechanoreceptors), increase in heart rate and blood pressure
Under-exposure to nicotine / tobacco and nicotine withdrawal symptoms	Affective symptoms : Irritability/anger/frustration, anxiety/anxious/nervous, depressed mood /depression/ sad/anhedonia, insomnia/sleep problems, dysphoria, hyperalgesia, impatient, restlessness, nightmares/ dreaming Somatic symptoms : tremors, bradycardia, gastrointestinal discomfort, nausea, constipation, increased appetite, hungry, weight gain, coughing, dizziness, sore throat, mouth ulcer Cognitive symptoms : difficulty concentrating, impaired memory
Hypersensitivity reactions	Susceptible consumers may experience hypersensitivity reactions such as skin disorders (e.g., localized or generalized rash, pruritus), urticaria and/or angioedema

8.2.6 Follow-up of Non-serious and Serious Adverse Events

Any non-serious AE that is ongoing during the passive safety FU will be actively followed-up by the Investigator during that period until it has been resolved, stabilized (i.e., no worsening of the condition), or an acceptable explanation has been found (e.g., a chronic condition).

At the end of the passive safety FU, all ongoing non-serious AEs will be documented as “ongoing” and no follow-up information will be sought for them anymore by the Investigator. At that point, the Investigator will assess whether the subject should be referred to his/her General Practitioner to have their ongoing AEs addressed accordingly.

All SAE will be followed up by the Investigator, despite their continuation after the end of the passive safety FU, until their resolution, stabilization (i.e., no worsening of the condition), or an acceptable explanation has been found (e.g., a chronic condition).

8.3 Reporting and Follow-Up of Serious Adverse Events

Any SAE observed during the period of collection by any of the parties involved in this study (including the Investigational site personnel) must be reported by that party within 24 hours of first awareness to UBC Pharmacovigilance, as described in the safety management plan (SMP).

SAEs considered related to the IP and observed by, or reported to, any of the parties involved in this study (including the Investigational site personnel) after the period of collection must also be reported by that party within 24 hours of first awareness to UBC Pharmacovigilance for safety surveillance purposes.

All the SAE report forms must be either faxed or sent as an attachment to an e-mail message to UBC Pharmacovigilance:

UBC Pharmacovigilance:	Fax number:	██████████
	E-mail:	██████████
	Address:	United BioSource Corporation UBC Pharmacovigilance [name] [name] Switzerland

As further information regarding an already reported SAE becomes known to any of the parties involved in this study, such follow-up information must be reported on a new SAE report form, marked as a follow-up report and submitted to UBC Pharmacovigilance according to the same timelines described above. The follow-up SAE report form must include the minimum information required for completion and only changed/new information needs to be specified. Information provided in the follow-up SAE report form generally supersedes any information that was initially reported.

The SAE report form to be used in this study is provided as a separate document. All SAEs will also be recorded on the relevant CRF page, in addition to the SAE report form.

The Investigator or designee is responsible for submitting the relevant reports of SAEs that occur during the study to the local IRB), according to local regulations and in line with the respective safety management plan.

If applicable, SAEs will be reported by Sponsor to the Center for Tobacco Products Office of Science within 15 days after the report is received by the Sponsor.

8.4 Reporting of Other Events Critical to Safety Evaluations

8.4.1 Abnormal Results of Laboratory Tests

Any clinical safety laboratory test result that is outside of the normal reference range will be reviewed by the Investigator and assessed for clinical significance according to its severity. The severity of abnormal laboratory test result must be assessed using CTCAE version 4.0 grading scale, available in [Appendix 3](#). Whenever that grading scheme is not available for the laboratory result of concern, the Investigator should assess the severity and the clinical significance of that result using his/her medical judgment.

Abnormal laboratory test results detected at the Screening Visit whose CTCAE grades are 2 or higher or still are CTCAE grade 1 and deemed clinically significant are usually concomitant disease or a manifestation of one and must be recorded accordingly. However, in some instances, they may be assessed as AEs (and therefore must be handled according to the directions from [Section 8.2](#) or as manifestations of already reported AEs). This decision will require a careful assessment of the abnormal result within the clinical context on a case-by-case basis and will depend on the Investigator's medical judgment.

Abnormal laboratory test results detected after the Screening Visit whose CTCAE grades are 2 or higher or still are CTCAE grade 1 and deemed clinically significant must be either recorded as AEs (and handled according to the directions in [Section 8.2](#)) or linked to a concomitant disease or still to an already reported AE.

The principles for assessing and reporting abnormal laboratory test results, emerging after the Screening Visit, using the CTCAE version 4.0 grading scale, are set up in [Table 4](#):

Table 4. Principles for Assessing and Reporting Abnormal Laboratory Test Results

Grading	Clinically significant?	Is it a worsening from previous results in study? [§]	Report?
Grade 1	No	Not applicable	No
Grade 1	Yes	No	No*
Grade 1	Yes	Yes	Yes, as AE or linked to an already reported AE
Grade 2 or higher	No/Yes	No	No*
Grade 2 or higher	No/Yes	Yes	Yes, as AE or linked to an already reported AE

* In this situation, this abnormal lab test result is either a manifestation of a concomitant disease or of an already reported AE.

[§] Grade increase in this context means the value is higher than the one from the screening visit.

Data and information contained in this document are considered to constitute trade secrets and confidential commercial information, and the legal protections provided to such trade secrets and confidential information are hereby claimed under the applicable provisions of US law. No part of this document may be publicly disclosed without the written consent of PMI.

Any other abnormal clinical laboratory result (including those that are not part of the core safety assessments) can, at the discretion of the Investigator, be reviewed and assessed. Even if they do not meet the criteria of the CTCAE grading scheme, the Investigator may consider them to be of clinical significance and, if they are, must report them as AEs.

In general, laboratory values will be recorded as “increased <lab parameter>” or “decreased <lab parameter>” to ensure consistency of recording/coding.

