2.3.2 Anticipated Foreseeable Risks due to Study Procedures

- Risks related to blood sampling, e.g., excessive bleeding, fainting, hematoma, paraesthesia, or infection.
- Risks related to drug application as part of testing procedures (i.e., spirometry with short-acting bronchodilator at Screening) per study protocol and scientifically accepted standards.
- The risk of procedures (e.g., blood drawing, spirometry) are deemed to be on a par with procedures routinely performed during normal or extended health examinations by the subject's healthcare professional. The total volume of blood planned to be drawn is approximately 434 mL and does not exceed the levels for a standard blood donation.
- Change in product use habits due to study requirements and related concomitant symptoms, e.g., craving, nicotine withdrawal symptoms.

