**ABNORMAL LABORATORY VALUES RATING: HEMATOLOGY PARAMETERS**

Hematology	Mild (Grade 1)	Moderate (Grade 2)	Severe (Grade 3)	Life- Threatening (Grade 4)
Anemia (Hemoglobin) ⁰ (g/dL) (mmol) (g/L)	<LLN-10.0 <LLN-6.2 <LLN-100	< 10-8.0 < 6.2-4.9 < 100-80	<8.0 <4.9 <80 Transfusion indicated	Life threatening consequences; urgent intervention indicated
Hemoglobin increase ⁰ - (g/dL)	Increase in >0 – 2 above ULN or above Baseline if Baseline is above ULN	Increase in >2 – 4 above ULN or above Baseline if Baseline is above ULN	Increase in >4 above ULN or above Baseline if Baseline is above ULN	-
WBC Decrease ⁰ - (cell/mm ³) (10 ⁹ /L)	<LLN – 3000; <LLN – 3.0	<3000 - 2000; <3.0 – 2.0	<2000 - 1000; <2.0 – 1.0	<1000; <1.0
Lymphocytes increase ⁰ (cell/mm ³)	-	>4,000 – 20,000	>20,000	-
Lymphocytes decrease ⁰ (cell/mm ³) (10 ⁹ /L)	<LLN – 800; <LLN – 0.8	<800 - 500; <0.8 – 0.5	<500 - 200; <0.5 – 0.2	<200; <0.2
Neutrophils Decrease ⁰ (cell/mm ³) (10 ⁹ /L)	<LLN – 1500; <LLN – 1.5	<1500 - 1000; <1.5 – 1.0	<1000 - 500; <1.0 – 0.5	<500; <0.5
Platelets decrease ⁰ (cell/mm ³) (10 ⁹ /L)	<LLN – 75,000; <LLN – 75.0	<75,000 – 50,000; <75.0 – 50.0	<50,000 – 25,000; <50.0 – 25.0	<25,000; <25.0

Abbreviations: LLN = Lower limit of the normal range; ULN = Upper limit of the normal range; WBC = White blood cell.

Data Source:

⁰ Common Terminology Criteria for Adverse Events (CTCAE) version 4.03. Toxicity Grading Scale for Healthy Adult and Adolescent Volunteers Enrolled in Preventive Vaccine Clinical Trials, U.S. Department of Health and Human Services, FDA, Center for Biologics Evaluation and Research - Guidance for Industry.

Data and information contained in this document are considered to constitute trade secrets and confidential commercial information, and the legal protections provided to such trade secrets and confidential information are hereby claimed under the applicable provisions of US law. No part of this document may be publicly disclosed without the written consent of PMI.

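### The Table 4 footnote on worsening, read literally as the laboratory value, reverses direction for decreases, conflicts with the paragraph above it, and names a different comparator from its own column

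*Protocol*

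**What the plan says.** All the reporting text is in Protocol Section 8.4.1.

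- **Severity scale.** "The severity of abnormal laboratory test result must be assessed using CTCAE version 4.0 grading scale". The grades are in Appendix 3.
- **Paragraph above Table 4.** It covers "Abnormal laboratory test results detected after the Screening Visit whose CTCAE grades are 2 or higher", and also Grade 1 results judged clinically significant. These "must be either recorded as AEs" or else be linked to a concomitant disease or an AE already reported. No direction of change is specified.
- **Table 4, deciding column.** The heading asks: "Is it a worsening from previous results in study". For Grade 2 or higher this column alone separates reporting from not reporting. For Grade 1 it does so once the result is clinically significant.
- **Footnote to that column.** "Grade increase in this context means the value is higher than the one from the screening visit".
- **Asterisk on the No outcomes.** "In this situation, this abnormal lab test result is either a manifestation of a concomitant disease or of an already reported AE".
- **Text after the table.** Results are to be entered as an increase or a decrease of the named parameter.

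Section 12.6.3 makes AE data the primary assessment of safety and gives laboratory AEs their own summary. It also plans change-from-baseline summaries and shift tables for laboratory data.

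**The concern.** The footnote opens with a grade increase but defines it by a higher *value*. Elsewhere the protocol uses that word for the laboratory result itself, for example in the Appendix 3 title and in the instruction on recording increases and decreases. For a parameter whose abnormality is a fall, a higher value is an improvement. Site staff who apply the footnote as written would therefore get the wrong answer from the table in both directions.

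The section presents Table 4 as the place where the reporting principles are set out, so it is the working tool for classification. Two investigators could classify the same fall differently, and laboratory AEs feed the primary safety assessment. Falls are not a remote case: Section 2.3.2 states "The total volume of blood planned to be drawn is approximately 434 mL", and the safety panel, which includes hematology, is repeated on Days 2 and 5.

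**Working it through.** The plan states no figure to reproduce. The check is a row count and an application of Table 4 under both readings of the footnote.

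**1. Graded rows in Appendix 3**

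| Panel | Rows | Rows grading a decrease |
|---|---|---|
| Clinical chemistry | 14 | 4 (sodium, potassium, glucose, albumin) |
| Hematology | 7 | 5 (hemoglobin, white cells, lymphocytes, neutrophils, platelets) |
| Urine | 1 | 0 |
| Total | 14 + 7 + 1 = 22 | 4 + 5 + 0 = 9 |

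**2. Two readings of the footnote**

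- Reading A: *value* is the laboratory result.
- Reading B: *value* is the CTCAE grade.

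**3. Application to hemoglobin**

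The results below are assumed for illustration. Appendix 3 grades hemoglobin below the lower limit of normal down to 10.0 g/dL as Grade 1, below 10 down to 8.0 as Grade 2, and below 8.0 as Grade 3.

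| Screening to Day 5 (g/dL) | Grades | Reading A | Reading B | Paragraph above Table 4 |
|---|---|---|---|---|
| 13.5 to 9.5 (new fall) | normal to 2 | 9.5 < 13.5: not a worsening, asterisked No | 2 > 0: worsening, Yes | Record as AE or link |
| 8.5 to 9.5 (partial recovery) | 2 to 2 | 9.5 > 8.5: worsening, Yes | 2 = 2: not a worsening, asterisked No | Record as AE or link to the existing condition |

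In the first row, Reading A contradicts the paragraph and Reading B agrees with it. In the second row, Reading A calls an improvement a worsening. Reading B gives the asterisked No, which is consistent with linking the result to a condition already on record.

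The same reversal applies to all 9 decrease rows under Reading A. For rows that grade increases, Reading A has a milder fault: any rise within one grade counts as a grade increase.

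**4. The comparator**

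This mismatch remains even under Reading B. Take an assumed result that is Grade 2 at Screening, Grade 1 on Day -2 and Grade 2 on Day 5.

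- Column heading (previous results in the study): 2 > 1 against Day -2, so a worsening.
- Footnote (Screening only): 2 = 2, so not a worsening.

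The heading and its own footnote give opposite answers.

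**The case against.** A reader might infer that falls in hemoglobin, neutrophils and the like will go unreported as AEs. The documents do not support that, and the case against it is strong.

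- The term being defined is a grade increase, in a table introduced as using the CTCAE scale, on which a deeper fall is a higher grade. Reading B is the more plausible intention.
- The paragraph above the table requires recording or linking whatever the direction.
- The asterisk presupposes a concomitant disease or an AE already reported. A new fall from normal need be neither, so it does not fit that outcome.
- The section provides for entries of decreased parameters, and the AE definition in Section 8.1.1 covers any worsening after consent.
- The change-from-baseline and shift tables in Section 12.6.3 display falls whether or not they are classed as AEs.
- The blood volume does not show that the footnote would bite. Section 2.3.2 says the volume stays within a standard donation, and the protocol gives no expected fall in hemoglobin. A Grade 1 fall judged not clinically significant is not reported under any reading.

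All of this stands and removes the claim of lost AEs. It does not remove the wording defect. Read literally, the footnote and the paragraph give opposite answers for a new Grade 2 fall. The asterisk does not prevent this, because it declares every such No to belong to a known condition even where none exists. The comparator mismatch is untouched by any of these arguments.

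**Conclusion.** The defect is real but minor. Under the literal reading, the footnote reverses the meaning of worsening for 9 of the 22 graded rows and conflicts with the paragraph directly above the table. Under the reading the drafters probably intended, that conflict disappears but the two comparators still disagree. What is at risk is consistent classification of laboratory AEs. No gap in AE capture is established.

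The size rests on the row count in Appendix 3. The hemoglobin and grade sequences are assumed examples and say nothing about how often such results would occur in 16 randomized subjects.

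**What to change.** Reword the footnote so that worsening means a higher CTCAE grade, in the direction of the abnormality, than at one named comparator. The sponsor should choose that comparator, either Screening or the most recent previous result in the study, and the column heading and footnote should both use it. The clause on direction matters because five parameters (sodium, potassium, glucose, hemoglobin and lymphocytes) are graded both high and low, so grades should be compared within the same Appendix 3 row.

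After the edit, check that table, footnote, asterisk note and paragraph give the same answer for a new Grade 2 fall and for a recovery within a grade. The cost is one sentence and a matching column heading. No data collection or analysis changes.

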8.4.2 Reporting Other Abnormal Findings

Other abnormal findings discovered during different clinical assessments (e.g., ECG, spirometry, physical examination, vital signs, body weight) should be evaluated for the clinical significance by the Investigator/designee based on his/her medical judgement. All abnormal clinical significant test results or clinical examination findings can, at the discretion of the Investigator, to be reported as AEs and handled according to the directions from [Section 8.2](#).

